Study Protocol and Statistical Analysis Plan

A Study to Compare Patient Perceptions of Two Different Hearing Aid Processing Philosophies

Version 1.0

September 13 2021

NCT04839289

Protocol Title

1 Background

Hearing aid brands vary in their DSP (Digital Signal Processing) strategies. For example, there are philosophical differences in processing when there is uncertainty of target location. One processing strategy aligns with a front facing target, whereas another aligns with the absence of a target in these situations. Despite the investigations regarding the different processing strategies, research has been limited as to how different populations perceive these different strategies in their daily life. Previous data gives insight to the different strategies in lab environments and simulated acoustic environments, but there is substantial need to investigate how these findings relate to the real world, which this study seeks to accomplish through the use of a home trial comparison.

2 Objectives

The primary objective of this study is to investigate whether individuals with moderate to severe hearing loss perceive a difference between Brand A and Brand B devices in their daily life.

3 Description of the investigational device

The investigational devices are intended for consumers with hearing loss, and provide amplification for soft, medium, and loud inputs using varying methods of compression and features. The devices will be used as intended for this investigation.

4 Design of the clinical investigation

This interventional study uses a within-subject, single blinded design with three conditions: Condition one consists of study hearing aid set A, condition two is study hearing aid set B, and condition three is study hearing aid set C. Sets A and C are the same hearing aids but will be different color casings. Twenty participants are planned.

5 Risks and benefits of the investigational device and clinical Investigation

Hearing aids enable people to hear sounds again, which could not be heard previously due to a hearing loss. The benefit of a compensated hearing loss results in a facet of multiple benefits which can be measured in different dimensions.

One of the main benefits of hearing aids is that they may enable people with a hearing loss to better and easier hear speech again, which is a fundamental ability to communicate and interact with others (e.g. family and friends, colleagues at work) in different listening situations in daily life.

The investigation carries risks typical to the standard of care for fitting and placing hearing aids in the ear. When placing a dome in the auditory canal, there is the risk of discomfort to the participant. There are risks of skin sensitivity to the material of the devices inserted into the auditory canal and behind the ear (pinna).

The risks of this study are minimal as the procedures are within the scope of practice of the

research audiologists. The participants may notice an improvement in hearing as compared to their own devices, or they may prefer their own devices to the study devices. The primary endpoint of subjective questionnaires and calculation of the Net Promoter Score will provide evidence for the perceived similarities or differences between the two study devices, as well as any preference for either device.

6 Endpoints

- SSQ (Speech Spatial Qualities) Questionnaire: Subjective ratings from 0 to 10 on various aspects of hearing aid performance in daily life, hearing speech in a variety of situations and contexts, spatial hearing, and overall qualities of hearing.
- Hearing Aid Satisfaction Score: Subjective ratings on overall satisfaction of devices. Ratings range from Very Satisfied (5) to Very Dissatisfied (1) for a number of hearing aid features, as well as performance in various listening situations.

7 Inclusion and Exclusion Criteria

Inclusion criteria for participant selection:

1. Experienced (6+ months) Phonak hearing aid users
2. N3-N4 binaural sensorineural hearing loss
3. Age 18 years and older

Exclusion criteria:

1. Conditions which may cause fluctuations in hearing (i.e. Meniere's)
2. Unable to tolerate the physical fit of RIC device with standard fit domes
3. Unable or unwilling to wear study devices for specified period of time, or inability to be seen for 4 study visits

8 Measurements and procedures

This study has a total of four visits.

Visit 1	Visit 2 (following Home Trial #1)	Visit 3 (following Home Trial #2)	Visit 4 (following Home Trial #3)
-Sound Quality Questionnaire for own devices -Hearing Aid Satisfaction survey for own devices -Three sets of hearing aids programmed for participant -Participant leaves with set A for home trial #1	-Sound Quality Questionnaire for Set A -Hearing Aid Satisfaction survey for Set A -Participant returns Set A and is sent home with Set B for home trial #2	-Sound Quality Questionnaire for Set B -Hearing Aid Satisfaction survey for Set B -Participant returns Set B and is sent home with Set A (Participant is told this is set C) for home trial #3	-Sound Quality Questionnaire for Set A -Hearing Aid Satisfaction survey for Set A -Participant returns set A and exits study

9 Statistical design and analysis

Fifteen to twenty participants are needed to determine significant differences between the study set A device and study set B device algorithms and sound quality. As the null

hypothesis (no difference will be detected) is the expected outcome, a smaller number of participants is acceptable. As this is an exploratory study, no a priori power analysis has been done.

Data collection will terminate once the acceptable number of participants has been recruited and have completed all three trials. As this is an observational study and done for internal purposes only, there is no statistical criteria for termination.

There are no planned objective tests for this study, therefore, all data collected will be subjective and qualitative in nature. Responses will be collected as question, response, and anonymous participant ID.

Responses to the subjective questionnaires will be analyzed using a repeated measures ANOVA test. The mean scores for each subsection of the sound quality questionnaire will be analyzed between the three test devices for all participants. The mean scores of each subsection of the sound quality questionnaire will also be analyzed between the three sets of study devices for all participants. Repeated measures ANOVA will also be used to determine if there are any individual differences between the brands. Aggregate data and individual HASS data will be analyzed using repeated measures ANOVA.

10 Investigation Duration

The expected duration of participation is six weeks.

11 Data Handling and Management

Study data is recorded both with paper and with electronic Case Report Forms (p/eCRF). For each enrolled study participant a CRF is maintained. All CRFs are kept current to reflect the subject's status at each phase during the course of study. Participants cannot be identified in the CRF by name or initials and birth date but an appropriate coded identification is used. All study team members are authorized for the CRF entries and it is assured that any unauthorized person can be identified both for pCRFs and eCRFs. If pCRFs are used, the investigator's acronym as well as the subject ID is filled in and data are entered into an electronic file for analysis by the respective investigator and data get monitored by the assigned monitor. In case of a self-evident corrections, either the subject does it by himself or the investigator undertakes the correction by crossing out the word/sentence with a single horizontal line and by adding the correction including his personal identifier and the date.

All paper data will be stored in a locked filing cabinet at the Phonak Audiology Research Center (PARC). All electronic data files will be encrypted and stored on secure research computers. All identifying data will be stored at PARC.

The identifiable data kept at PARC will be destroyed as soon as the final analyses have been completed. The de-identified data will be kept for seven years after the publication of results. When the data are destroyed, paper records will be shredded by services provided at PARC. Electronic data will be encrypted as de-identified NOAH packages, where applicable, to be shared with Sonova Switzerland.

12 Amendments to the CIP

Amendments to the CIP, if necessary, will be updated with justification in this document.

13 Deviations from clinical investigation plan

Deviations from the CIP to protect the rights, safety and well-being of human participants under emergency circumstances may proceed without prior approval of the sponsor and the EC— such deviations will be documented and reported to the sponsor representative (Study Manager) and the EC as soon as possible. Apart from that the investigator is not allowed to deviate from this CIP unless that deviation does not influence the investigation data.

Each deviation from the CIP will be documented including date of protocol deviation, name of investigator, participant ID, affected visit (if applicable), reason for deviation and anticipated influence on investigation data. Each deviation needs to be reported to the Sponsor (= Study Manager) and depending on the severity, also to the IRB.

14 Device accountability

The PI or authorized designee keep records documenting the following in a written process:

- Names of participants who received, used, returned, or disposed of device
- Date of receipt, identification, and quantity of each investigational device (batch/serial number or unique code)
- Expiry date (if applicable)
- Date(s) of use
- Participant identification
- Date on which the device was returned (if applicable)
- Date of return of unused, expired, or malfunctioning investigational devices (if applicable)
- Date and documentation of disposal of devices as per sponsor instructions (if applicable)

15 Informed consent process

At the beginning of the first appointment, investigators will hand the consent form to the participant in a private setting and grant sufficient time to read the whole form. The consent form contains detailed information about incentives and reimbursement. Any questions will be answered and the participant will be given sufficient time to decide whether or not they want to participate in the study. After the participant signed two copies of the consent form, the researcher will sign both copies as well and provide one copy to the participant.

In case of changes to the procedures described in the consent form, the participant will be informed at the beginning of an appointment. Informed Consent will only be obtained by investigation participants who can provide informed consent themselves before enrollment.

16 Adverse events, adverse device effects and device deficiencies

Device deficiencies and all **adverse events (AE)** including all **serious adverse events (SAE)** are collected, fully investigated and documented in the source document and appropriate case report form (CRF) during the entire investigation period, i.e. from participant's informed consent until the last protocol-specific procedure, including a safety follow-up period (ISO_14155, 2020). Documentation includes dates of event, treatment, resolution, assessment of seriousness and causal relationship to device and/or investigation procedure.

Information on AEs is systematically collected during the regular investigation visits, and phone calls (if applicable).

The causality assessment of the SAE will be conducted according to MDCG 2020-10/1 Safety Reporting in Clinical Investigations of Medical Devices under Regulation (EU) 2017/745.

The reporting of Serious Adverse Events and Device Deficiencies follows the Regulation (EU) 2017/745 and the MDCG 2020-10/1 Safety Reporting in Clinical Investigations of Medical Devices under Regulation (EU) 2017/745.

17 Vulnerable Populations

The investigation does not include any vulnerable populations.

18 Suspension or premature termination of the clinical investigation

The clinical investigation will be suspended or prematurely terminated if a study device malfunctions or if the participants or researchers are exposed to safety risks other than those outlined in this document. These events may include but are not limited to natural disaster, widespread outbreak of illness, compromised structure of the investigation site, etc.

There is a blinding code kept electronically with the study materials. This code can be used to link the participant with their study ID, if needed.

According to the FDA, follow-up is required for participants who experience serious adverse events. Follow-up will be conducted by the study manager until the nature of the event is resolved.

19 Publication policy

The clinical investigation will be registered in clinicaltrials.gov, a publicly accessible database, as required by US law.

The results of the clinical investigation will be documented as an internal report only.

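### Casing colour appears tied to set and is not balanced across participants, so any average colour preference would enter the A-C check and the three-set ANOVA, and A versus B if B's colour differs from A's

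*Combined protocol and SAP*

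**What the plan says.** Section 4 describes a within-subject, single-blinded study with three conditions and says of the sets: "Sets A and C are the same hearing aids but will be different color casings". It does not give set B's colour, and it does not say whether a given colour goes with the same set for every participant.

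The objective in Section 2 is whether participants "perceive a difference between Brand A and Brand B devices in their daily life". Section 6 describes the satisfaction score as "Subjective ratings on overall satisfaction of devices", scored 1 to 5. The items are not listed. Section 9 confirms that there are no objective tests.

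Section 8 fixes the order for everyone. At Visit 1, "Participant leaves with set A for home trial #1"; set B follows; at Visit 3 the participant is "sent home with Set A (Participant is told this is set C) for home trial #3".

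Section 9 says that subsection means of the sound quality questionnaire "will be analyzed between the three test devices for all participants", and that "Aggregate data and individual HASS data will be analyzed using repeated measures ANOVA". No colour or period term is named.

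**The concern.** Issuing the same aid twice gives the study a built-in control: A versus C shows how far ratings move when the device has not changed. The different casing exists to disguise the repeat. If colour stays with the set, the disguise also puts a systematic difference into that control.

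Every outcome is a rating by someone who may see the casing. If participants on average like one colour better, the preference is carried into the set means, and the three-set ANOVA has no term that could separate it. Section 9 expects no difference, so a spurious positive is the more damaging error here. Changing the order of the sets would not cure this, because colour would still travel with the set. If colour never varies within a set, no later analysis can separate the two.

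**Working it through.** **No plan figure to reproduce.** Section 9 asks for 15 to 20 participants and states that no power analysis was done. It gives no effect size, SD or alpha.

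**Inputs.** From the document: n = 20 (Section 4), three sets, repeated measures ANOVA. Assumed: two-sided 5% level; average colour shift δ of 0.2, 0.3 or 0.5 points on the 1-5 scale; SD of the within-person A-C difference s of 0.6, 0.8 or 1.0; independent errors; no true device or period effect. The document supports no particular δ, and zero is possible.

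**1. A versus C, colour fixed to set.** Paired t on 19 df, noncentrality δ√n/s. For δ = 0.3 and s = 0.6 this is 0.3 × 4.472/0.6 = 2.24. Chance of a significant A-C difference:

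| δ | s = 0.6 | s = 0.8 | s = 1.0 |
|---|---|---|---|
| 0.2 | 29% | 19% | 14% |
| 0.3 | 56% | 36% | 25% |
| 0.5 | 94% | 76% | 56% |

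**2. Three-set F, only set C shifted (B shares A's colour).** Residual variance is s²/2. With means 0, 0, δ, the sum of squares about their mean is 2δ²/3, so λ = n(2δ²/3)/(s²/2) = 4nδ²/(3s²), on 2 and 38 df. For δ = 0.3:

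- s = 0.6: λ = 7.2/1.08 = 6.67, giving 60%
- s = 0.8: λ = 7.2/1.92 = 3.75, giving 37%
- s = 1.0: λ = 7.2/3.00 = 2.40, giving 25%

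A separate simulation at δ/s = 0.5 (the first line above) also gave 60% at n = 20, and 46% at n = 15.

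**3. Colour bias left in each contrast** (the liked colour adds δ; entries are sizes, ignoring sign):

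| Allocation | A-C | A-B | B versus mean(A,C) |
|---|---|---|---|
| Fixed: C liked, A and B in the other colour | δ | 0 | δ/2 |
| A and C swapped 10:10, B in the other colour throughout | 0 | δ/2 | δ/2 |
| A and C swapped 10:10, B split 10:10 | 0 | 0 | 0 |

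In the second row the swap puts bias into A-B where there was none. By simulation at δ/s = 0.5 and n = 20, B versus mean(A,C) is then falsely significant in 22% of studies without a colour term.

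**4. Cost of a colour term**, from the within-person design matrix at n = 20:

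- A/C-only swap with B in one of the two colours: variance × 1.00 for A-C, × 1.25 for A-B, × 1.33 for B versus mean(A,C).
- A/C swap with B split evenly: colour is orthogonal to set, so × 1.00 for all three contrasts. Residual df fall from 38 to 37.

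Without a colour term, the swap turns the colour effect into noise in A-C. With δ = 0.3 and s = 0.80 the variance is 0.64 + 0.09 = 0.73, so the SD is 0.85.

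**5. Period.** Home trial 1 is always A and home trial 3 is always A relabelled as C. With no colour effect at all, a linear trend totalling 0.5 s across the three trials makes the three-set F significant in 48% of simulated studies. Colour balancing leaves this untouched.

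**The case against.** The strongest reply is that no route from colour to outcome is documented. Appearance is not named as a satisfaction item, and the other questionnaire rates speech, spatial hearing and sound qualities. The percentages also need a non-zero average preference: if some participants like one colour and others the other, fixed colours add noise but no mean shift. Both points stand. They make the size unknown and keep the priority low, but they do not show the effect to be absent, because overall satisfaction with a worn device can respond to its look.

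A fixed colour per set for everyone is also a natural reading and not stated text. Section 8 blurs it by sending the participant home with set A under the name C, where Section 4 implies a separately coloured set. The two sections should be reconciled.

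A reader might infer that an A-C difference caused by colour would be reported as a brand difference. The document does not support that, because A and C are the same aid. A reader might also infer that the Brand A versus Brand B comparison is certainly contaminated; that depends on B's colour, which is not given. Finally, the fixed order without a period term is the larger weakness. That is true, but correcting it would leave the colour problem in place.

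**Conclusion.** The point holds in a limited form. Colour differs between A and C, no balancing is described, and the analysis has no colour term. If colour is fixed to set, an average colour preference enters the A-C control and the three-set F, and enters A versus B only if B's colour differs from A's. Under the assumed 0.3-point shift, with SD 0.6 to 1.0 and n = 20, false significance of the three-set F is 25% to 60%. These rates illustrate a mechanism and do not estimate what will happen.

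A reader might infer that swapping the A and C colours removes the problem at almost no cost. It does so only for the A-C mean; the primary comparison is cleared only if B joins the allocation, and the document does not say that B comes in the same colours. Nor would balanced colours make A-C a clean benchmark, since it still contains any change from home trial 1 to home trial 3. For an exploratory, internal study this is a worthwhile optional change.

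**What to change.** In Section 4:

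- State the casing colours of all three sets.
- Alternate by participant number which of two colours is issued as set A and which as set C (10 participants each way at n = 20).
- Split set B over the same two colours, half the participants each, so that every set is seen equally often in each colour.
- Record the colour worn in each home trial.

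In Section 9, add a colour term to the repeated measures model.

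If B is not available in those colours, say so. Where B shares one of the two colours, swap A and C and keep the colour term, accepting about 25% more variance for A versus B. Where B has its own colour, brand and colour cannot be separated, and this should be reported as a limitation.

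The cost is one code to track, possibly some spare casings, and 1 degree of freedom. A and C still differ in colour within each participant, so the disguise is kept. The fixed order needs its own remedy.

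### Section 9 compares three 'devices' although two are the same hearing aid, and specifies no Brand A versus Brand B contrast within that test

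*Combined protocol and SAP*

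**What the plan says.** **Objective.** Section 2 asks "whether individuals with moderate to severe hearing loss perceive a difference between Brand A and Brand B devices in their daily life". No other objective is given.

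**Conditions.** Section 4 names three hearing aid sets, then adds that "Sets A and C are the same hearing aids but will be different color casings". The Section 8 visit table fixes the order for everyone as A, B, A. At Visit 3: "Participant returns Set B and is sent home with Set A (Participant is told this is set C) for home trial #3". Brand A is therefore rated at Visits 2 and 4, and Brand B at Visit 3.

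**Analysis.** Section 9 frames the sample size around the two brands: "Fifteen to twenty participants are needed to determine significant differences between the study set A device and study set B device". It then applies repeated measures ANOVA to the mean of each sound quality subsection across three test devices, and repeats this in nearly the same words for three study sets. A further sentence says the same method will look for brand differences at the individual level. Aggregate and individual HASS data are also to go through repeated measures ANOVA, without saying across which conditions. No contrast, no rule for combining the two A periods and no alpha are given.

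**Net Promoter Score.** Section 5 says "The primary endpoint of subjective questionnaires and calculation of the Net Promoter Score will provide evidence for the perceived similarities or differences". This is its only mention. Section 6 lists two instruments: "SSQ (Speech Spatial Qualities) Questionnaire: Subjective ratings from 0 to 10 on various aspects of hearing aid performance in daily life", and a satisfaction score of which it says "Ratings range from Very Satisfied (5) to Very Dissatisfied (1) for a number of hearing aid features". The visit table schedules only those two kinds of form, for example "Sound Quality Questionnaire for Set A -Hearing Aid Satisfaction survey for Set A".

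**The concern.** A three-level test asks whether any of the three mean ratings differ. Here two of the three come from the same hearing aid, worn in the first and third home trials. If participants become more or less generous over time, or respond to the casing colour or the new label, those two ratings will differ and the test may reject. That says nothing about whether Brand A and Brand B are perceived differently.

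This matters more because Section 9 expects no difference to be found. The behaviour of the test when the devices are equivalent is then its most important property. A significant three-level result could be reported as a brand difference when it is a period effect. Two analysts following Section 9 could also choose different brand comparisons: A at Visit 2 only, A at Visit 4 only, or both.

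**Working it through.** **1. The plan's own figure.** The 15 to 20 participants of Section 9 cannot be reproduced. No alpha, effect size or SD is given, and the section says no power analysis was done. What follows is illustration with assumed inputs.

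**2. What the three-level test contains.** It has 2 degrees of freedom, which split into two orthogonal parts:

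- B at Visit 3 minus the mean of A at Visits 2 and 4. This bears on the objective.
- A at Visit 4 minus A at Visit 2. This compares one device with itself.

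Only the first part concerns the brands, but either can make the test significant.

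**3. Inputs.** n = 20 (Sections 4 and 9) or 15 (Section 9). Assumed: two-sided alpha 0.05, three ratings per person in order A, B, A, and independent normal within-person errors with SD 1. Effects are in units of that SD.

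**4. Formulas.**

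- Three-level test: F with 2 and 2(n−1) degrees of freedom and noncentrality λ = n × Σ(period mean − grand mean)².
- Contrast: one-sample t on B − (A1 + A2)/2. Its variance per person is 1 + 1/4 + 1/4 = 1.5, so the noncentrality is δ × √(n/1.5), where δ is the true value of the contrast.

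**5. Numbers put in.**

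- Drift 0.2 per period, means 0, 0.2, 0.4: λ = 20 × (0.04 + 0 + 0.04) = 1.6; δ = 0.2 − 0.2 = 0.
- Drift 0.4 per period, means 0, 0.4, 0.8: λ = 20 × (0.16 + 0 + 0.16) = 6.4; δ = 0.
- Device effect 0.5, means 0, 0.5, 0: λ = 20 × 0.25 × 2/3 = 3.33; δ = 0.5, noncentrality 0.5 × √(20/1.5) = 1.83.
- One-off shift of 0.4 after period 1, means 0, 0.4, 0.4: λ = 20 × 0.16 × 2/3 = 2.13; δ = 0.4 − 0.2 = 0.2, noncentrality 0.2 × √(20/1.5) = 0.73.

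Simulated rejection rates (100,000 trials per setting); the exact noncentral distributions agree to within about 0.2 percentage points:

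| Assumed truth | Three-level, n=20 | Contrast, n=20 | Three-level, n=15 | Contrast, n=15 |
|---|---|---|---|---|
| No device effect, drift 0.2 per period | 17.5% | 5.0% | 14.0% | 5.0% |
| No device effect, drift 0.4 per period | 57.8% | 5.1% | 44.4% | 5.1% |
| No device effect, one-off shift 0.4 | 22.1% | 10.6% | 17.2% | 9.1% |
| Device effect 0.5, no drift | 32.7% | 40.9% | 25.0% | 31.3% |

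**6. Where the power gain comes from.** B at Visit 3 minus A at Visit 2 alone has variance 2, so its noncentrality at n=20 is 0.5 × √(20/2) = 1.58 and its power is 32% (25% at n=15). That is no better than the three-level test. The gain to 41% comes from using both A ratings.

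**7. Sensitivity to the unit.** If 0.5 is read in SDs of the paired A-B difference (error variance 0.5), power at n=20 is 60% for the three-level test, 56% for a single A rating and 69% for the pooled contrast (46%, 44% and 55% at n=15). The ranking in favour of the pooled contrast is unchanged.

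**8. Net Promoter Score.** No arithmetic applies. Section 5 relies on it as evidence on differences and preference. Section 6 does not list it, Section 8 does not schedule it, and Section 9 does not analyse it. No item, cut-off or formula appears anywhere.

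**The case against.** - **Section 9 is not silent on scores or brands.** A reader might infer that it names no score and no brand comparison. It does name scores: subsection means, and aggregate and individual HASS data. It also has the sentence on brand differences and a sample-size statement about set A and set B. This stands. What is missing is narrower: the contrast, and the role of the two A periods. The brand sentence supplies neither.
- **HASS.** The three-condition wording is attached to the sound quality questionnaire only. It should not be read into the HASS sentence.
- **Drift is assumed.** No document reports a drift of 0.2 or 0.4 SD per period. This stands, so the rejection rates show what can happen and are not a forecast. With no drift, both tests hold about 5%.
- **Power.** A reader might infer that the absence of a contrast itself costs power. Step 6 shows it does not.
- **Exploratory status.** Section 9 calls the study exploratory and internal. A missing single primary score or multiplicity rule is therefore not a defect that the documents support. However, the section also says it will determine significant differences between A and B, and that aim needs a stated contrast.
- **Net Promoter Score.** A reader might infer that it forms part of the primary endpoint and will never be collected. The Section 5 sentence can also mean evidence beside the questionnaires, and a recommend item may sit in a survey that is not reproduced. The supported point is only that the sections do not connect.

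**Conclusion.** The concern holds in this form: Section 9 plans a three-condition comparison for a two-brand objective, and specifies neither an A-versus-B contrast within it nor how the two periods on the same device represent Brand A. A significant result from that test need not concern the brands.

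Under the stated assumptions, in particular independent errors and an assumed drift, the wrong answer could arise in about 14% to 18% of studies at a drift of 0.2 SD per period, against 5% with the planned contrast. The gain in power from pooling both A ratings is about 6 to 8 percentage points at a 0.5 SD effect (31.3 − 25.0 = 6.3 at n=15; 40.9 − 32.7 = 8.2 at n=20). The structural point does not depend on these figures.

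The contrast is not a full remedy. With a fixed A-B-A order it removes only a linear time trend, and it rejects about 11% of the time under an assumed one-off 0.4 SD shift after the first period (n=20). The Net Promoter Score is a secondary inconsistency between sections and does not carry the point.

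**What to change.** 1. In Section 9, make the brand comparison for each score the within-person contrast of B at Visit 3 minus the mean of the A ratings at Visits 2 and 4, with a 95% interval and a stated alpha.
2. Report A at Visit 4 ('set C') minus A at Visit 2 separately, as a check on how far ratings of identical devices differ.
3. State in Section 9 that, because the order is fixed, the contrast removes a linear time trend only.
4. Reconcile Section 5 with Sections 6, 8 and 9: either identify the item that yields the Net Promoter Score, with its cut-offs and formula, and report it descriptively, or delete it from Section 5.

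Naming one primary score is optional in this exploratory study.

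The cost is a few lines of text. No visits or participants are added, and the contrast uses only ratings already scheduled.

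### Every participant wears the sets in the same order (A, B, then A relabelled C), so Brand B is always home trial 2 and cannot be separated from a non-linear order effect

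*Combined protocol and SAP*

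**What the plan says.** Section 2 sets the primary objective: whether people with hearing loss "perceive a difference between Brand A and Brand B devices in their daily life".

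Section 4 describes the design: "This interventional study uses a within-subject, single blinded design with three conditions". It adds that "Sets A and C are the same hearing aids but will be different color casings". There are therefore two devices under three labels.

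The visit table in Section 8 fixes the order:

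- Visit 1: "Three sets of hearing aids programmed for participant", then "Participant leaves with set A for home trial #1".
- Visit 2: "Participant returns Set A and is sent home with Set B for home trial #2".
- Visit 3: "Participant returns Set B and is sent home with Set A (Participant is told this is set C) for home trial #3".

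Section 9 plans a repeated measures ANOVA. Subsection means "will also be analyzed between the three sets of study devices for all participants", and a further sentence says the same method will look for differences between brands. No section mentions randomised or counterbalanced order, a washout, or a period or order term.

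**The concern.** Brand and home trial are the same variable under this plan: trial 2 is Brand B for everyone, and trials 1 and 3 are Brand A for everyone. The outcomes are subjective ratings collected over consecutive home trials, so they could move with order for reasons unrelated to brand, such as adjustment to the first study set. Any such movement that is not a straight line across the three trials goes into the brand comparison. It can create a brand difference that does not exist or cancel one that does. The second risk matters here because Section 9 expects the null result, and a null produced by cancellation would look like confirmation.

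The hidden duplicate helps only in part. A against C compares trial 1 with trial 3. It can show that ratings shifted between those trials, but it cannot correct the estimate for B or detect an effect confined to trial 2.

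**Working it through.** **Inputs.** From the documents: 20 participants planned (Section 4), 15 to 20 regarded as sufficient (Section 9), three home trials in the order A, B, A (Section 8). Section 9 says no power analysis was done, so there is no planned figure to reproduce. Assumed: two-sided 5% level; independent, equal-variance errors within a participant with SD σ; order effects of size g from 0.25σ to 1.0σ. Call the effects of trials 1 to 3 p1, p2, p3.

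**Can brand be estimated?** Participant (20 columns), three-level period (2) and brand (1) make 23 columns.

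| Design | Period term | Columns | Rank |
|---|---|---|---|
| Fixed A-B-A | three levels | 23 | 22 |
| Fixed A-B-A | linear | 22 | 22 |
| Six orders | three levels | 23 | 23 |

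Under the fixed order, brand is estimable only if the period effect is assumed linear.

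**Bias without a period term.**

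- B minus the mean of A and C: bias p2 − (p1 + p3)/2, variance σ²(1 + 1/4 + 1/4)/n = 1.5σ²/20 = 0.075σ², SE 0.2739σ. The bias is zero for a linear drift.
- B minus first A: bias p2 − p1, SE √(2/20)σ = 0.3162σ. A linear drift biases this one too.
- Three-set F test: noncentrality 20·Σ(p − p̄)²/σ². For (0, g, g) this is 20 × (2/3)g² = 13.33g² with g in units of σ, which is 0.83, 3.33 and 13.33 at g = 0.25, 0.5 and 1.0.

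**Rejection rates with identical brands, n = 20.** F uses 2 and 38 df; the contrasts are t tests on 19 df.

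| Order effect | Test | g = 0.25 | g = 0.5 | g = 1.0 |
|---|---|---|---|---|
| (0, g, g) | three-set ANOVA | 11% | 33% | 89% |
| (0, g, g) | B vs first A | 12% | 32% | 85% |
| (0, g, g) | B vs mean of A and C (bias g/2) | 7% | 14% | 41% |
| (0, g, 0) | B vs mean of A and C (bias g) | 14% | 41% | 93% |

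The ANOVA figures arise partly because A then differs from C. B against the second A trial stays at 5% under (0, g, g). With 15 participants and g = 0.5 and 1.0 under (0, g, g), the ANOVA rejects in 25% and 77%, and the pooled contrast in 11% and 31%.

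**Does A against C give warning?** Under (0, g, g) it is significant in 32% (g = 0.5) and 85% (g = 1.0) of studies. Under (0, g, 0) it is significant in 5%, which is chance. In 39% (g = 0.5) and 89% (g = 1.0) of simulated studies under (0, g, 0), the pooled contrast was significant and A against C was not.

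**Masking.** Take a true B effect of −0.5σ. With no order effect, the pooled contrast has 41% power. Under (0, 1, 1)σ the bias is +0.5σ, the two cancel, and power is 5%.

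**Six orders, allocated 4/3/4/3/3/3, with three-level period and set.** In 40,000 simulated studies per scenario, the pooled contrast's false-positive rate was 4.9% to 5.2% over both patterns at g = 0.5 and 1.0. Bias was below 0.003σ. Power for −0.5σ under (0, 1, 1)σ was 43%.

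**The case against.** The strongest case against this has five parts.

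- **Section 9 also mentions brands.** Since A and C are the same device, a brand comparison would naturally pool them, which cancels linear drift. That is a fair reading, but the pooling is not written down, and pooling does not remove curvature.
- **The sizes are assumed and the largest are extreme.** This stands. Under the only mechanism named, adjustment to the first study set, the pooled contrast carries just g/2. The masking example is built to cancel exactly. Participants are experienced users who also rate their own aids at Visit 1, so the real effect may be small. Nothing in the documents shows that it is.
- **The precision claim depends on exchangeable errors.** This also stands. With serial correlation of 0.1, 0.2 or 0.3, the six-order SE is about 3%, 7% or 11% larger than that of A-B-A. The planned repeated measures ANOVA itself assumes exchangeability. Nor does randomising add power: with 38 df for the fixed-order contrast and no order effect, power at 0.8σ is 81.2%, against 81.0% for six orders on 36 df.
- **Randomising may expose the duplicate.** Four of the six orders put A and C back to back, which is 13 of 20 participants under 4/3/4/3/3/3 and none today. This is a real cost of unknown size. The casings do differ in colour.
- **The study is exploratory and internal.** That lowers the consequences of a wrong answer, but it does not change which comparison the design can identify.

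**Conclusion.** The concern holds. The written procedure ties Brand B to home trial 2 for everyone, so the primary question can be answered only by assuming that order effects are linear (for the pooled contrast) or absent (for the three-set ANOVA). The size of the error is unknown. Over an assumed range of 0.25σ to 1.0σ, the pooled contrast's false-positive rate is 7% to 41% for a first-trial effect and 14% to 93% for an effect confined to trial 2. The confounding itself rests on no assumption. Because it cannot be undone after data collection and is cheap to avoid beforehand, it should be corrected before enrolment.

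**What to change.** **Change.**

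1. At Visit 1, randomise each participant in balanced blocks to one of ABC, ACB, BAC, BCA, CAB, CBA; for 20 participants, for example, 4/3/4/3/3/3.
2. In Section 9, fit participant, period (three levels) and set (three levels). Name B against the mean of A and C as the brand test, and report C minus A as the same-device check.
3. Reword the Section 8 table so that each visit's questionnaires refer to the set just worn and the participant leaves with the next set on the list.

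Blocking and the period term both matter. Unblocked randomisation raises the SE by about 3% on average at n = 20 (9% at the 95th percentile). Omitting period leaves the test conservative.

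**Cost.** A randomisation list, sequence tracking and edited visit wording. All three sets are already programmed at Visit 1, so no extra device, visit or participant is needed. Residual df fall from 38 to 36. The brand SE goes from 0.2739σ to 0.2742σ (up to 0.2752σ, depending on which two orders take the extra participant), and the SEs of B − A and C − A stay at 0.316σ to 0.317σ. Carry-over is not removed. A device carry-over term becomes estimable, at about 12% to 13% in SE, whereas the fixed order cannot estimate it at all.

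**If the order cannot be changed,** prespecify the pooled contrast and state the confounding as a limitation. That holds first-trial bias to g/2 but does not remove it.
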